3.1.6 Data Coordinating Center (DCC)

The DCC's primary responsibility will be to manage data operations, monitor adherence to the study protocol and implement the data analysis plan. Responsibilities will include:

- Developing, implementing, and monitoring the data and safety monitoring plan, the data management plan, and the randomization plan
- Overseeing training of clinical site staff with regard to data entry, data correction, and randomization procedures
- Assisting CCC on development of data collection form templates and overseeing the implementation of paper-based and web-based forms
- Monitoring completion and timeliness of form submissions and query responses
- Developing and implementing data edit specifications
- Monitoring distribution of data queries to clinical sites
- Monitoring sites' responsiveness to queries
- Participating in quality assurance visits to the clinical sites
- Preparing reports on study progress and study results for the DSMB (twice per year and on request), the NIA (annually and on request), IRBs (annually and on request), and the SC (on request)
- Preparing final data files and performing data analyses for publications and presentations
- Preparing data files for the EEC and to be shared with any ancillary studies that are approved by the SC

- Developing and maintaining a website to ensure up-to-date study documents (e.g., data collection forms, manuals, protocol, study personnel contact information)

Data capture, data management, and randomization will be implemented through a subcontract with Axio Research, LLC (hereafter referred to as Axio) in Seattle, WA.

3.1.7 Economic Evaluation Core (EEC)

The EEC will be responsible for assessing the cost-effectiveness of the interventions. The economic value of the interventions will be determined by assessing the impact on QALYs, cost, and cost per QALY gained over the study period. The EEC will conduct analyses of within trial comparisons for the economic endpoints (costs and QALYs) as well as develop and implement a decision-analytic modeling framework that will incorporate within trial findings regarding costs and QALYs.

3.2 Scientific Oversight

3.2.1 Scientific Oversight Committees (SOC)

There are four SOCs that will provide scientific oversight for distinct aspects of the trial. CCC and DCC staff and SOC leadership will provide day-to-day guidance on issues pertaining to the implementation procedures for recruitment, measurement, intervention delivery, and data management and analysis. SOCs will perform their responsibilities under the guidance of the SC and with assistance from CCC and DCC personnel. The areas of responsibility and membership of each committee are described briefly below.

Recruitment and Evaluation

The Recruitment and Evaluation SOC will refine and optimize procedures and strategies for recruitment and retention of study participants and for maintaining adherence to the protocol. It will be this group's responsibility to oversee recruitment progress at all sites, intervene in cases of under-recruitment, and report recruitment progress to the SC. The committee will oversee retention efforts and investigate and intervene when a site is having retention problems. A study management database will be developed by the CCC to provide a standardized way for clinical sites to monitor study-related activities in a timely way (see section Section 16:). The Recruitment and Evaluation SOC will utilize reports from this database which will allow monitoring of recruitment, retention, and data collection by clinical site. Another responsibility of this committee is ensuring that protocols are followed for data collection procedures and that each clinical site establishes standard operating procedures and maintains a current version throughout the study. The Recruitment and Evaluation SOC will also monitor data collection for the CAP study and approved ancillary studies. This committee will be led by the director of the CCC and will include the clinical site PIs and the director of the EEC.

Clinical Direction

The Clinical Direction SOC will contribute to protocol implementation from the perspective of orthopaedic surgery and clinical gerontology, reviewing clinical practice-related issues and overseeing the clinical safety of all study participants. The group will monitor the scientific literature, scientific meetings, and input received from colleagues on medical topics that are relevant to the project and advise the SC on emerging scientific issues that may affect the conduct of the study. Committee members will be on call on a rotating basis to answer questions about eligibility from clinical staff and to serve as Independent Safety Monitors (ISMs) to review RAEs. They may be asked to provide medical advice in study-related emergencies

and to address IRB issues related to participant safety.

Intervention

The Intervention SOC will finalize and refine the intervention protocols and work closely with the CCC and clinical sites to ensure the QC procedures and training for the intervention. The committee will develop the Intervention Manual, and together with the Recruitment and Evaluation SOC, will implement strategies to enhance and monitor treatment fidelity and adherence to the interventions. This committee will be responsible for selecting, training, and certifying all PTs involved in the intervention protocols.

Publications and Ancillary Studies Committee (PASC)

The PASC will be responsible for: (a) encouraging production of high quality publications and presentations in a timely fashion, (b) encouraging broad participation by the study investigators in publications, abstracts, and presentations, c) reviewing ancillary studies with regard to scientific value and participant burden, paying particular attention to avoiding interference with the main study, and (d) assuring accurate maintenance of a database on study publications, presentations and ancillary studies. The PASC will review proposals for and final versions of research abstracts, presentations, manuscripts to be submitted to journals, and proposals for ancillary studies. The PASC will report its recommendations to the SC for ratification. Standing members will include two committee co-chairs, and the study chair and co-chair of the SC. Additional committee members will be recommended by standing members; at a minimum, the directors of the DCC and CCC will each be invited to nominate one representative to serve as a standing member of the PASC.

3.2.2 Specialized Support for Exercise and Nutrition

This advisory committee will provide guidance and expertise to the SC and Oversight Committee Chairs in the areas of exercise and nutrition in older adults as required during the development of the protocol, MOP, and training materials; execution of the project; and interpretation of study findings as they relate to the interventions. The committee will convene on an as-needed basis at the request of the SC. This advisory committee will be involved in providing guidance on the development and implementation of the dietician protocol and will work closely with the Intervention Oversight Committee to ensure the successful and safe implementation of the interventions.

3.2.3 UMB Investigational Drug Services (IDS)

The University of Maryland IDS will be responsible for the purchasing, distributing, and accounting procedures for all investigational drugs within the University of Maryland Medical Center campus and will be responsible for preparing and shipping the vitamins/supplements for this project to each of the clinical sites. The vitamins/supplements for the study will be purchased and managed through the University of Maryland IDS. IDS will prepare “treatment kits” for each randomized participant that will include all vitamins/supplements for the 16-week study period:

- 1.) 2000 IU vitamin D3, one tablet daily
- 2.) 600 mg calcium, one tablet daily
- 3.) Multivitamin, one tablet daily

Each treatment kit will contain four individual packs numbered 1-4. Each pack contains a 4-week supply of vitamin D3, calcium, and a multivitamin. The IDS will prepare appropriate packaging for each item in the treatment kit, with a label and directions for taking each product that complies with legal requirements. Participants who have contraindications for calcium supplementation (i.e., calculated creatinine clearance < 30 ml/min, elevated total or ionized

calcium, history of kidney stones, primary hyperparathyroidism, or sarcoidosis) will not be given calcium.

[figure not shown]
3.2.4 Study Clinical Sites

The study has three collaborating clinical sites each with a clinical site PI and coordinator. The three clinical sites are Arcadia University (AU), University of Maryland Baltimore (UMB), and University of Connecticut Health Center (UCHC).

Responsibilities of the clinical site PI (with assistance from the coordinator) will include:

- Maintaining cooperation of study hospitals and other recruitment sites and ensuring that medical staff involved with the care of hip fracture patients are well informed about the trial
- Recruiting study participants according to the study protocol
- Ensuring retention and adherence of study participants
- Performing all study-related assessments (including complete tracking of outcomes during follow-up)
- Overseeing completion of data collection forms, enrolling participants using the automated randomization system, and entering data and processing data edit queries
- Training and supervising staff at the clinical site; assigning tasks to data collectors, PTs, and dieticians; and providing day-to-day supervision of their work
- Protecting participant safety and verifying that informed consent procedures are followed according to Good Clinical Practice guidelines
- Properly maintaining all clinical site study materials and records
- Reporting all RAEs and protocol deviations
- Participating in the study oversight committees and manuscript preparation

3.3 Organizational Chart

Section 4: Study Objectives

4.1 Primary Objective

The primary objective will be to determine if a specific multi-component 16-week intervention based on aerobic conditioning, specificity of training, and muscle overload (the PUSH intervention), initiated up to 26 weeks following admission to the hospital for hip fracture, will be more successful in producing community ambulation at 16 weeks after study entry (approximately six months post-fracture) compared to a non-specific multi-component intervention of transcutaneous electrical nerve stimulation (TENS), flexibility activities, and AROM exercises (the PULSE intervention).

The primary hypothesis is that there will be a 20 percentage point or greater difference in the proportion of PUSH compared to PULSE participants who achieve community ambulation 16 weeks after randomization. Community ambulation will be defined as walking at least 300 meters in six minutes on the Six-Minute Walk Test (SMWT).

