The other clinical trials began six months or later after hip fracture, with interventions that included various combinations of strengthening exercise, balance training, functional training, and AROM/flexibility. Three of these included endurance training but lacked at least one of the other components of the program we are proposing. Results show positive outcomes in terms of function, gait speed, balance, strength, and endurance.^{22,29,63-68} A study conducted in a gym demonstrated improvement in self-reported outdoor mobility in the intervention group who were four years post-fracture, but no changes in dynamic balance or walking speed.⁶⁹ Since hip fracture recovery is reported to plateau at six months (which is when the interventions in these studies began), the results of these studies are comparable to the exercise findings reported in older adults without hip fracture, i.e., that older adults benefit from increased activity. These studies indicate that use of higher intensity exercise with endurance training beginning six months post-fracture reduces impairments in precursors to community ambulation.

The unanswered question is whether a higher intensity program performed as soon as usual care is complete will return more people to community ambulation. Mangione described a program that provided function, strength, balance, and endurance training to a single patient three months post-fracture.⁷⁰ The patient showed dramatic improvements in all physical precursors to community ambulation. In addition, the recent pilot study of the intervention resulted in a significant between-group difference in distance walked on the SMWT.

A limited number of studies have examined exercise programs post-hip fracture. The most successful in terms of strength, balance, and gait speed outcomes were completed over a 6-month time period in an exercise center.^{22,68} The majority of the research published is fraught with problems including lack of control groups, small samples, and inadequate exercise dose. Prior research suggests that more intensive multi-component training as soon as usual care is complete should be safe and effective.

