11.4 Timing of Study Procedures

The target date for completion of the pre-randomization (i.e., screening) assessments will be anchored to the date of admission to the hospital for hip fracture. The target date for completion of all other assessments will be anchored to the date of randomization (see Table 1).

Table 1. Timing of Study Procedures

PROCEDURE	TARGET DATE	ALLOWABLE INTERVAL
Phase 3 screening	As early as possible following admission	Up to 26 weeks post-admission
Baseline assessment	As early as possible following admission	Up to 26 weeks post-admission
Randomization	As early as possible following admission	Up to 26 weeks post-admission
Dietitian consult	1 week post-randomization	+1 week
First intervention visit	1 week post-randomization	+16 weeks
First telephone interview	4 weeks post-randomization	-1 week, +3 weeks
Subsequent telephone interviews	At 4-week intervals from date of randomization	-1 week, +3 weeks
First follow-up assessment	16 weeks post-randomization	+2 weeks
Out-of-window assessment	16 weeks post-randomization	0-16 weeks and 18-38 weeks post-randomization

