15.6 Sample Size Adequacy

15.6.1 Primary Aim

The original power calculations for this study were based on the assumption of a 10% loss to follow-up and a 10% rate of nonadherence. However, based on data on the first 88 study participants, the estimated rate of loss to follow-up was 6.8% and the rate of nonadherence was 12.2%. These estimates were used to revise the power calculations using a new total sample size of 210.

The threshold defined for the primary outcome, the ability to walk 300 meters or more in six minutes, was exceeded by approximately 9% of subjects in the BHS 4 cohort at six months post-fracture (which corresponds approximately to the 16-week post-randomization follow-up in the proposed trial). Furthermore, 23% of controls in the pilot study for the current project surpassed the 300 meter threshold. The midpoint of this range (9% to 23%) is 16% and this was

used as the basis for power calculations for the primary outcome, using the R version 2.10.1.²¹³ Binder et al,⁶⁸ using a comparable intervention, reported an effect size of approximately 0.6 SD on a continuous measure of physical performance. The 0.6 SD effect size corresponds to a difference in six-minute walk distances of about 50 meters for hip fracture patients; a 50-meter difference has been determined by Perera et al.¹⁸³ to be clinically meaningful. Assuming normal distributions for the SMWT, and with 16% surpassing the 300 meter threshold in the PULSE group at 16 weeks, a 0.6 SD effect size projects to a 19 percentage point difference in the proportion of community ambulators between the PUSH group and the PULSE group. A difference of 20 percentage points or more in the proportion of participants achieving community ambulation is thus considered an achievable and clinically meaningful goal.

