1.1.2 Secondary Analyses of Primary Outcome

In a secondary analysis, an alternative outcome variable will be created to represent the participant's community ambulation status at 16-week follow-up. This secondary variable will take the value of 'yes' if the participant was tested with the SMWT and walked 300 m or more in six minutes. The secondary variable will take the value of 'no' if 1) the participant was tested with the SMWT and walked less than 300 m in six minutes, 2) the participant was not tested with the SMWT and adjudication resulted in the participant's being classified as a treatment failure because of death, sickness, or gait speed < 0.6 m/s, or 3) the participant was tested with the SMWT but not according to protocol and adjudication resulted in the participant's being classified as a treatment failure, whatever the reason. The secondary variable will take the value of 'missing' if 1) the participant was not tested with the SMWT and adjudication resulted in the participant's being classified as a treatment failure based only on self- or proxy-reported walking limitation or 2) the participant was not tested with the SMWT (or the participant was tested but not according to protocol) and adjudication resulted in the participant's being classified as 'indeterminate'. All participants, including those with a missing value for the alternative outcome variable, will be included in the secondary analysis. Weights will be used to adjust for covariate imbalances between the groups due to chance or differential rates of indeterminate outcomes. For the PUSH group, the weight for each observation will be defined as the inverse probability that an observation would be assigned to the PUSH group given the covariates for that observation. This will effectively up-weight observations from groups with lower probability of being in PUSH. Similarly, for the PULSE group, the weight for each observation will be defined as the inverse probability that an observation would be assigned to the PULSE group given the covariates for that observation. The probability of being assigned to PUSH (or PULSE) will be estimated as a function of covariates based on a logistic regression model. Candidate variables for creating the weights will include age, sex, and type of hip fracture; baseline BMI, MNA[®]-SF score, CES-D score, 3MS score, distance walked in six minutes on SMWT, SPPB score, mPPT score, NHATS balance score, gait speed on 50-ft fast walk, and gait speed on 4-m usual walk; and the presence of cardiac disease, pulmonary disease, diabetes, and history of stroke or TIA at baseline. Variables will be ranked for inclusion based on the Beach-Meier approach (Beach 1989). A common rule of thumb for logistic regression models is that there should be at least 10 events and 10 non-events for every covariate in the model. We will follow that rule of thumb (based on the number of community ambulators observed in our sample) in deciding how many covariates to include in the model used to estimate weights.

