1.1.3 Assessment of effect modification by site, period, and patient characteristics

Study site will be investigated as a modifier of the effect of the intervention by testing a site-by-intervention interaction term on the risk difference scale based on a binary regression model

with an identity link. If there is evidence that study site is an effect modifier (i.e., $p < 0.1$ for the interaction term), we will report site-specific treatment effects.

In the fall of 2014, a decision was made to modify the frequency of intervention visits during the first 8 weeks from 3 per week to 2 per week. We will assess the impact of this protocol change on the intervention outcomes in a secondary analysis. To do so, assuming no significant interaction between site and intervention group, we will assess the statistical significance of the interaction between the period during which the participant was randomized (before vs after the protocol change) and treatment group. If there is a significant interaction, then we will make separate treatment group comparisons in the two periods (one comparison for participants randomized during the period when there were three sessions per week and another for participants randomized during the period when there were two sessions per week).

In addition, a series of analyses will be performed to examine the differential impact of the PUSH intervention relative to the PULSE intervention in subgroups defined by participant characteristics. To do this, a variable-by-intervention interaction term will be tested for each of the following variables:

1. Gender
2. Age at baseline (≥ 85 years versus 60-84 years)
3. Baseline depression (CES-D score ≥ 16 versus CES-D score < 16)
4. Baseline balance confidence (with median Activities-Specific Balance Confidence scale score as the cutpoint to define the subgroups)
5. Baseline nutritional status (MNA®-SF score < 8 versus MNA®-SF score ≥ 8)
6. Baseline cognitive status (3MS score < 91 versus 3MS score ≥ 91)
7. Baseline physical performance (SPPB score < 7 versus SPPB score ≥ 7)

If the interaction term for any of these subgroup variables is significant, results will be presented separately in strata of the subgroup variable.

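### The 16-week outcome is described as about six months after fracture, but entry up to week 26 lets it fall as late as week 42, and no planned analysis uses time since admission

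*Protocol*

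**What the plan says.** Protocol 4.1 describes the PUSH intervention as "initiated up to 26 weeks following admission to the hospital for hip fracture" and, in the same sentence, gives the outcome as "community ambulation at 16 weeks after study entry (approximately six months post-fracture"). The 26-week limit recurs in 6.1, 6.2, exclusion criterion 4.5 and Table 1 ("Up to 26 weeks post-admission"). No lower limit is stated.

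Protocol 15.6.1 relies on the same equivalence. It takes a rate of about 9% from an earlier "cohort at six months post-fracture (which corresponds approximately to the 16-week post-randomization follow-up in the proposed trial"), pairs it with 23% among the pilot controls, and uses the midpoint, 16%, as the PULSE rate.

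Protocol 5.2 gives the rationale. The open question is "whether a higher intensity program performed as soon as usual care is complete will return more people to community ambulation". Trials that began at six months or later are described separately: "Since hip fracture recovery is reported to plateau at six months (which is when the interventions in these studies began").

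Randomisation is blocked within site only (6.2) and the primary test is unadjusted (Protocol 15.1, SAP 1.1.1). In SAP 1.1.3 "a variable-by-intervention interaction term will be tested for each of the following variables": gender, age, depression, balance confidence, nutrition, cognition and SPPB. Site and visit-frequency period are tested as well. In SAP 1.1.2, "Candidate variables for creating the weights will include age, sex, and type of hip fracture", followed by 14 further baseline measures; SAP 1.4 repeats the list. Time from fracture or admission is in none of these lists, nor among the descriptive characteristics in Protocol 10.5.1.

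**The concern.** The primary endpoint is anchored to randomisation, but the objective and the sample-size basis describe it by time since fracture. That description is inaccurate for anyone who enters well after week 10. A participant randomised at week 26 is already at six months on the day of entry.

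Two things are at stake. First, readers may take the result to describe walking ability six months after fracture, or the effect of early treatment, when some participants may have been treated and tested considerably later. The 9% six-month cohort rate may likewise not apply to late entrants. Second, the protocol gives reason to expect recovery stage to matter, and the interval is needed for every participant to check criterion 4.5. Yet the plan neither describes it by arm nor allows it to enter the covariate-adjusted secondary analyses.

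**Working it through.** **Timing.** Let t be weeks from admission to randomisation.

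- Outcome time after admission = t + 16 weeks.
- Six months is about 26 weeks, so the description fits at t = 26 − 16 = 10.
- At the limit: 26 + 16 = 42 weeks (about 9.7 months).
- With the +2-week window in Table 1: 26 + 18 = 44 weeks (about 10.1 months).
- Table 1 also allows an out-of-window assessment up to 38 weeks after randomisation: 26 + 38 = 64 weeks.

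Weeks run from admission; time from fracture is the same or slightly longer.

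**Share tested later than week 26.** This is the share with t > 10. The documents do not give the entry distribution, so these are assumptions:

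| Assumed entry (uniform) | Share with t > 10 | Mean outcome time |
|---|---|---|
| Weeks 0–20 | 10/20 = 50% | 10 + 16 = 26 weeks |
| Weeks 0–26 | 16/26 = 62% | 13 + 16 = 29 weeks |
| Weeks 4–26 | 16/22 = 73% | 15 + 16 = 31 weeks |

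The first row corresponds to the 20-week limit that the summary of modifications records before Version 6.0. Table 1 sets the target as early as possible, so entry may cluster early and all three shares may be too high. Allowing four weeks' tolerance around six months, the third row falls to 12/22 = 55%.

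**The plan's power.** Inputs from 15.6.1: 105 per arm, 6.8% loss, 12.2% non-compliance, 2.4% inflation for the sequential design, 16% versus 36%, one-sided 0.025.

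- Effective n per arm = 105 × 0.932 / 1.024 = 95.6.
- PUSH rate after non-compliance = 0.16 + 0.20 × 0.878 = 0.336.
- Power by the two-proportion normal formula = 80.8%. Simulation with the Table 4 boundaries gives 80.1%. Table 5 states 80%.

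The stated figure reproduces. It does depend on the control rate. For the same 20-point difference, power is 89% at a control rate of 9% and 74.5% at 23%, the two ends of the plan's own range. At an assumed 30% it is 70.5%. These figures only illustrate sensitivity, because the documents give no rate for weeks 27 to 44. The direction is also unclear: later testing allows more recovery, but inclusion criterion 3.3 selects late entrants who still cannot walk 300 m.

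**Precision of an early–late contrast.** After 6.8% loss there are 210 × 0.932 / 4 ≈ 49 per cell. With rates of 16% and 36%,

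SE = √[2 × (0.16 × 0.84 + 0.36 × 0.64) / 49] = √(2 × 0.3648 / 49) = 0.122, about 12 percentage points.

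For 80% power at two-sided 0.05, the interaction would have to be (1.96 + 0.84) × 0.122 ≈ 34 points. For a 20-point interaction, power is Φ(0.20/0.122 − 1.96) ≈ 37%.

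**The case against.** The strongest reply is that the six-month phrase is only an approximate gloss. Wherever the endpoint operates (the primary hypothesis in 4.1, Protocol 15.1, SAP 1.1.1) it is 16 weeks after randomisation, and the entry range is disclosed in the same sentence as the gloss. That stands: no test is defined by time since fracture, and the analysis text promises no six-month or early-treatment claim.

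The protocol's account of recovery is also mixed. Section 5.2 puts the plateau at six months, but 5.1 says that gait speed does not level off until almost a year, which would place week 42 before the plateau. A reader might infer that the trial pools people still recovering steeply with people who have stopped recovering. The documents do not establish that. Section 5.2 also frames its question by the end of usual care, not by a date before a plateau.

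Recovery stage is partly covered. Baseline six-minute distance, SPPB, mPPT, balance and two gait speeds are candidate covariates, and SPPB is a tested modifier. These measure current level, however, and two people at the same distance in weeks 6 and 25 may be on different courses. The documents do not show how much the interval would add. The period interaction is no substitute: the summary of modifications shows that Version 6.0 changed visit frequency and extended the entry limit together, so that term cannot separate them.

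Finally, an interaction test would reveal little and would be a tenth unadjusted one after site, period and seven characteristics. That also stands, and it is why the analysis should be exploratory.

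**Conclusion.** The point holds as a matter of description and of one omitted baseline variable. The six-month statement in 4.1 and 15.6.1 fits entry near week 10 only; the design allows the outcome as late as week 42, or 44 with the window. How many participants this affects cannot be known from the documents, and 50% to 73% are results of assumed entry patterns, not estimates. No planned analysis uses time since admission.

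Three stronger readings are not supported. A reader might infer that the treatment comparison is biased; it is not, because allocation is random and concurrent within site. A reader might infer that the sample size is wrong; the stated power reproduces, and no control rate for late entrants is given that would contradict 16%. A reader might infer that most participants are tested after six months; that depends on an entry distribution that is not reported. What the design does not support is the stated timing itself, or a six-month or early-post-fracture conclusion drawn without looking at the observed intervals.

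**What to change.** 1. In Protocol 4.1 and 15.6.1, replace the six-month description with the range that the design allows, and note that the six-month cohort rate may not apply to late entrants. Report, by arm, the observed distribution of weeks from admission to randomisation and from admission to the 16-week test.
2. Add weeks from admission to randomisation to the candidate covariates in SAP 1.1.2 and 1.4. The SAP already caps the number of covariates by its ten-events rule and ranks the candidates, so the models need not grow.
3. Optionally, report the interval as an exploratory continuous effect modifier on the risk-difference scale, with estimate and confidence interval. State that precision is low (SE about 12 points for an early–late contrast) and that it adds one more unadjusted interaction test.
4. Word any conclusion about timing to match the observed distribution.

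The cost is wording and a few lines of analysis. No new data are needed, because criterion 4.5 already requires the interval. The primary test, its boundaries and the sample size stay as they are.
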